16.5 Monitoring

By signing this protocol, the Investigator grants permission to the Sponsor (or designee), and appropriate regulatory authorities to conduct on-site monitoring and/or auditing of all appropriate study documentation. Monitoring visits will be conducted by representatives of the Sponsor according to the U.S. CFR 21 Part 312 and International Conference on Harmonisation (ICH) Guidelines for GCP (E6) and to ensure investigator compliance to 21 CFR Parts 50, 56 and 312 and to GCP.

16.6 Subject Confidentiality

In order to maintain subject confidentiality, only a site number, subject number and subject initials will identify all study subjects on CRFs and other documentation submitted to the Sponsor. If specific consent is given, the subject's CFF patient registry number will also be collected. Additional subject confidentiality issues (if applicable) are covered in the Clinical Study Agreement.

17 ADMINISTRATIVE, ETHICAL, REGULATORY CONSIDERATIONS

The study will be conducted according to the Declaration of Helsinki, Protection of Human Volunteers (21 CFR 50), Institutional Review Boards (21 CFR 56), and Obligations of Clinical Investigators (21 CFR 312).

To maintain confidentiality, all laboratory specimens, evaluation forms, reports and other records will be identified by a coded number and initials only. Clinical information will not be released without written permission of the subject, except as necessary for monitoring by the FDA. The Investigator must also comply with all applicable privacy regulations (e.g., Health Insurance Portability and Accountability Act of 1996, EU Data Protection Directive 95/46/EC).

17.1 Protocol Amendments

Any amendment to the protocol will be written by the Sponsor. Protocol amendments cannot be implemented without prior written IRB/IEC approval except as necessary to eliminate immediate safety hazards to patients. A protocol amendment intended to eliminate an apparent immediate

hazard to patients may be implemented immediately, provided the IRBs are notified within five working days.

17.2 Institutional Review Boards and Independent Ethics Committees

The protocol and consent form will be reviewed and approved by the IRB/IEC of each participating center prior to study initiation. SAEs regardless of causality will be reported to the IRB/IEC in accordance with the standard operating procedures and policies of the IRB/IEC, and the Investigator will keep the IRB/IEC informed as to the progress of the study. The Investigator will obtain assurance of IRB/IEC compliance with regulations.

Any documents that the IRB/IEC may need to fulfill its responsibilities (such as protocol, protocol amendments, Investigator's Brochure, consent forms, information concerning patient recruitment, payment or compensation procedures, or other pertinent information) will be submitted to the IRB/IEC. The IRB/IEC's written unconditional approval of the study protocol and the informed consent form will be in the possession of the Investigator before the study is initiated. The IRB/IEC's unconditional approval statement will be transmitted by the Investigator to the Sponsor or designee prior to the shipment of study supplies to the site. This approval must refer to the study by exact protocol title and number and should identify the documents reviewed and the date of review.

Protocol and/or informed consent modifications or changes may not be initiated without prior written IRB/IEC approval except when necessary to eliminate immediate hazards to the patients or when the change(s) involves only logistical or administrative aspects of the study. Such modifications will be submitted to the IRB/IEC and written verification that the modification was submitted and subsequently approved should be obtained.

The IRB/IEC must be informed of revisions to other documents originally submitted for review; serious and/or unexpected adverse experiences occurring during the study in accordance with the standard operating procedures and policies of the IRB; new information that may affect adversely the safety of the patients of the conduct of the study; an annual update and/or request for re-approval; and when the study has been completed.

17.3 Informed Consent Form

Informed consent will be obtained in accordance with the Declaration of Helsinki, ICH GCP, US Code of Federal Regulations for Protection of Human Subjects (21 CFR 50.25[a,b], CFR 50.27, and CFR Part 56, Subpart A), the Health Insurance Portability and Accountability Act (HIPAA, if applicable), and local regulations.

The Investigator will prepare the informed consent form, assent and HIPAA authorization and provide the documents to the Sponsor or designee for approval prior to submission to the IRB/IEC. The consent form generated by the Investigator must be acceptable to the Sponsor and be approved by the IRB/IEC. The written consent document will embody the elements of informed consent as described in the ICH and will also comply with local regulations. The Investigator will send an IRB/IEC-approved copy of the Informed Consent Form to the Sponsor (or designee) for the study file.

A properly executed, written, informed consent will be obtained from each subject prior to entering the subject into the trial. Information should be given in both oral and written form and subjects (or their legal representatives) must be given ample opportunity to inquire about details of the study. If appropriate and required by the local IRB/IEC, assent from the subject will also be obtained. If a subject is unable to sign the ICF and the HIPAA authorization, a legal representative may sign for the subject. A copy of the signed consent form (and assent) will be given to the subject or legal representative of the subject and the original will be maintained with the subject's records.

During the course of the study, if modifications are made to the consent form that impact the subject, the subject will be re-consented as described above.

17.4 Consent for Collection and Use of CFF Registry ID Number

To facilitate possible future evaluation of retrospective and prospective information from all patients who screen for this study, consent will also be sought to collect the subject's CFF Registry ID number at the screening visit. The CFF registry collects data on all CF patients who consented to participate in the CFF registry and who are followed at CFF-accredited care centers. The registry data includes information from clinical encounters, hospitalizations courses of antibiotics, and year-end surveys. Data also include microbiology results, spirometry results, CF genotype and other information. If specific consent is given to collect this number, the patient's CF registry number will be recorded in the CRF.

17.5 Publications

The preparation and submittal for publication of manuscripts containing the study results shall be in accordance with a process determined by mutual written agreement among the study Sponsor and participating institutions. The publication or presentation of any study results shall comply with all applicable privacy laws, including, but not limited to, the Health Insurance Portability and Accountability Act of 1996.

17.6 Investigator Responsibilities

By signing the Agreement of Investigator form, the Investigator agrees to:

1. Conduct the study in accordance with the protocol and only make changes after notifying the Sponsor (or designee), except when to protect the safety, rights or welfare of subjects.
2. Personally conduct or supervise the study (or investigation).
3. Ensure that the requirements relating to obtaining informed consent and IRB review and approval meet federal guidelines, as stated in § 21 CFR, parts 50 and 56.
4. Report to the Sponsor or designee any AEs that occur in the course of the study, in accordance with §21 CFR 312.64.
5. Ensure that all associates, colleagues and employees assisting in the conduct of the study are informed about their obligations in meeting the above commitments.
6. Maintain adequate and accurate records in accordance with §21 CFR 312.62 and to make those records available for inspection with the Sponsor (or designee).

7. Ensure that an IRB that complies with the requirements of §21 CFR part 56 will be responsible for initial and continuing review and approval of the clinical study.
8. Promptly report to the IRB and the Sponsor (or designee) all changes in the research activity and all unanticipated problems involving risks to subjects or others (to include amendments and IND safety reports).
9. Seek IRB approval before any changes are made in the research study, except when necessary to eliminate hazards to the patients/subjects.
10. Comply with all other requirements regarding the obligations of clinical investigators and all other pertinent requirements listed in § 21 CFR part 312.

APPENDIX 1. SCHEDULE OF EVENTS

	VISIT 1 SCREENING DAY (-42 THROUGH -1) ^a	VISIT 2 DAY 0	PHONE CALL/ CONTACT WEEK 4 DAY 28 ±7	PHONE CALL/ CONTACT WEEK 8 DAY 56 ±7	VISIT 3 WEEK 12 DAY 84 ± 7 DAYS	PHONE CALL/ CONTACT WEEK 16 DAY 112 ±7	PHONE CALL/ CONTACT WEEK 20 DAY 140 ±7	VISIT 4 WEEK 24 DAY 168 ± 14 DAYS	FOLLOW UP CALL/ CONTACT OR VISIT 5 WEEK 26 DAY 182 ± 14 DAYS ^b	EARLY PERMANENT DISCONTINUATION OF STUDY TREATMENT ^c
Informed Consent ^d	X ^e									
Review Eligibility	X ^e	X ^f								
Medical History and Demographics	X ^e									
Adverse Events Review			X	X	X	X	X	X	X	X
Concomitant Medication Review	X	X ^f	X	X	X	X	X	X	X	X
Cystic Fibrosis GI Parent Questionnaire		X			X			X		X
Height and Weight	X	X ^f			X			X		X
Complete Physical Exam	X ^g									
Abbreviated Physical Exam		X ^f			X			X		X
Dispense Fecal Collection Kit (x2 Vials)	X ^a	X			X					
Fecal Elastase ^h	X									
Obtain Frozen Fecal Specimen: • Fecal calprotectin • Banking (Optional)		X ^f			X			X		X
Vital Signs and Oximetry		X ^f			X			X		X
Spirometry (in subjects ≥ 4 years of age at the time of randomization)		X ^f			X			X		X
Obtain Blood Specimen: • On-site Clinical Laboratory (see protocol section 9.2)		X ^f						X	X ^b	X

	VISIT 1 SCREENING DAY (-42 THROUGH -1) ^a	VISIT 2 DAY 0	PHONE CALL/ CONTACT WEEK 4 DAY 28 ±7	PHONE CALL/ CONTACT WEEK 8 DAY 56 ±7	VISIT 3 WEEK 12 DAY 84±7 DAYS	PHONE CALL/ CONTACT WEEK 16 DAY 112 ±7	PHONE CALL/ CONTACT WEEK 20 DAY 140 ±7	VISIT 4 WEEK 24 DAY 168 ± 14 DAYS	FOLLOW UP CALL/ CONTACT OR VISIT 5 WEEK 26 DAY 182 ± 14 DAYS ^b	EARLY PERMANENT DISCONTINUATION OF STUDY TREATMENT ^c
Obtain Blood Specimen: • Redox/ Metabolomics • Banking (Optional)		X ^f						X		X
Randomization		X ^f								
Study Drug Administration		X ⁱ								
Study Drug Dispensing		X			X					
Study Drug Accountability					X			X		X
Provide Subject Diary		X			X					
Subject Diary Review					X			X		X
Antibiotic Utilization Assessment			X	X	X	X	X	X	X	X

^a Visit 1(Screening) and Visit 2 can be combined if a fecal specimen is obtained prior to dosing.

^b Any subject with any clinically significant abnormal lab results or on-going treatment-related AEs at Visit 4 will return for a follow-up visit. All other subjects will receive a phone call follow-up to document any new adverse events and changes to concomitant medications. Safety labs will only be performed if the subject had clinically significant abnormal labs (with an exception of hs-CRP) at Visit 4 (see protocol section 9.2).

^c These visit procedures should be followed for subjects who discontinue study drug treatment early.

^d Informed Consent for the study will be obtained; an optional consent for specimen banking will be obtained to participate in specimen banking and for provision of CFF registry number.

^e Perform procedure at combined Visit 1 and Visit 2.

^f Procedures and collections performed prior to first dose of study drug.

^g If Visit 1 and Visit 2 are combined Complete Physical Exam is performed instead of Abbreviated Physical Exam.

^h Only subjects without a historical fecal elastase test to document pancreatic insufficiency.

ⁱ First dose of study drug should be administered in clinic at Visit 2 (or combined Visit 1 and Visit 2) post blood and fecal specimen collection. Study drug should be administered orally three times a day with meal/snack for 168 ± 14 days.

APPENDIX 2: DEFINITION OF PULMONARY EXACERBATION

The presence of a pulmonary exacerbation is established by the following:

- (1) One of the major criteria alone
or
- (2) Two of the minor signs/symptoms and fulfillment of symptom duration

Major Criteria: *(One finding alone establishes the presence of a pulmonary exacerbation)*

- (1) Absolute decrease in FEV₁ %predicted of $\geq 10\%$
- (2) Oxygen saturation $< 90\%$ on room air *or* absolute decrease of $\geq 5\%$
- (3) New lobar infiltrate(s) or atelectasi(e)s on chest radiograph
- (4) Hemoptysis (more than streaks on more than one occasion in past week)

Minor Signs/Symptoms: *(Two minor signs/symptoms are required in the absence of major criteria. If at least 2 minor signs/symptoms are present, at least one needs to be 3 or more days in duration to meet the PE definition)*

- (1) Increased work of breathing or respiratory rate
- (2) New or increased adventitial sounds on lung exam
- (3) Weight loss $\geq 5\%$ of body weight or decrease across 1 major percentile in weight percentile for age in past 6 months
- (4) Increased cough
- (5) Decreased exercise tolerance or level of activity
- (6) Increased chest congestion or change in sputum

1.1 Study Rationale and Design

The nutritional status of children with cystic fibrosis (CF) has a profound impact on their mortality and morbidity. Optimal nutrition in the early years of life has a positive influence on long-term growth, development and improved pulmonary status later in life. Despite pancreatic enzyme supplementation, high calorie diets, and supplementation of fat-soluble vitamins, many children with CF fail to achieve optimal growth. In CF, intestinal inflammation and dysbiosis contribute to impaired digestion, absorption, and nutrient utilization. CF caregivers have emphasized the importance of achieving good nutritional status with routine evaluation and aggressive nutritional interventions very early in life. Reducing intestinal inflammation may be a crucial factor in achieving this goal.

Among the interventions studied to combat the underlying mechanisms of malnutrition are anti-oxidants, including glutathione. Early studies have shown that people with CF have decreased systemic levels of glutathione. It is not known whether this is the result of inflammatory mediators suppressing production or secretion of glutathione, or involves loss of a possible function of cystic fibrosis transmembrane conductive regulator (CFTR) to transport glutathione across the cell membrane. Glutathione has both antioxidant and mucolytic properties in patients with CF. In two pilot studies, orally administered glutathione improved growth in people with CF. One of these studies evaluated the effect of reduced glutathione on the growth of 44 patients with CF in a single center placebo-controlled, randomized, double blind clinical trial. Participants receiving supplemental glutathione over a six-month period experienced an average increase of 0.67 SD in weight-for-age z-score compared to an average of 0.1 SD improvements in weight-for-age z-score in participants receiving placebo. Furthermore, improvements in body mass index (BMI) and height as well as reduced fecal calprotectin were also observed. These encouraging results emphasize the need to study the impact of oral glutathione on growth in CF patients in a larger, multi-center study.

The purpose of this randomized, placebo-controlled (Phase II) study will be to further evaluate the effects of oral glutathione on growth in children with CF.

The GROW study is a prospective, multi-center, randomized, placebo-controlled, double-blind, Phase II clinical trial. Approximately sixty pancreatic insufficient (PI) participants with CF who are ≥ 2 and < 11 years of age will be enrolled to receive either L-Glutathione Reduced (GSH) or placebo given orally three times a day for 24 weeks. Each participant will be seen for four study visits: Visit 1 (Screening), Visit 2 (Baseline/Randomization, Day 0), Visit 3 (Week 12) and Visit 4 (Week 24). At Visit 2, participants will be randomized to receive either active treatment or placebo. Visit 1 and Visit 2 may be combined if participant meets eligibility requirements and a fecal specimen is collected prior to dosing. Safety and clinical outcomes will be assessed throughout the study. Assessment of inflammatory and other bio-markers in blood and fecal specimens will be performed at Visit 2 and Visit 4.

The primary objective of this study is to investigate the effect of 24 weeks of treatment with oral glutathione on change in weight-for-age z-scores. The secondary objectives are to evaluate

changes in other clinical outcomes (growth, lung function, gastrointestinal (GI) symptoms, hospitalizations, antibiotic utilization and pulmonary exacerbations [PE]) as well as to evaluate changes in blood and fecal inflammatory markers.

1.2 Interim Data Monitoring Committee Reviews

Oversight for this trial is provided by a Data Monitoring Committee (DMC) with members from the Cystic Fibrosis Foundation Therapeutics (CFFT) Data Safety Monitoring Board (DSMB). Abbreviated data summaries are provided to the DMC in periodic interim safety reports, and one more comprehensive interim report.

The purpose of the interim reviews is to monitor enrollment and feasibility, as well as patient safety. The abbreviated safety reports will include a summary of screening, enrollment metrics, baseline characteristics, participant withdrawals and study drug discontinuation, drug compliance (for completed participants), protocol violations, and AEs and SAEs tabulated by treatment group.

The comprehensive interim report expands on the contents of the abbreviated safety reports to include efficacy summaries. The emphasis of the comprehensive report is primarily on safety; however, formal group sequential monitoring of the primary endpoint will be conducted. Please note that informal comparisons of the data between treatment arms must be carefully interpreted in this report given that complete follow up data is not available for all participants.

2. Report Generation

2.1 Data Flow

An electronic data capture system, Medidata Rave, will be utilized for collection of study data. The Investigator will prepare and maintain adequate and accurate source documents designed to record all observations and other pertinent data for each participant who signs informed consent.

Study personnel at each site will enter data from source documents corresponding to a participant's visit or assessment into the protocol-specific electronic Case Report Form (eCRF). Participants will not be identified by name in the study database or on any study documents to be collected by the Sponsor (or designee), but will be identified by a site number, participant number, and initials. If a correction is required for an eCRF, the time and date stamp will track the person entering or updating eCRF data and an electronic audit trail is created.

The data will be entered into a validated database. The DCC will be responsible for data processing, in accordance with procedural documentation. All procedures for the handling and analysis of data will be conducted using good computing practices for the handling and analysis of data for clinical trials.

Once data have been entered into the study database, a system of computerized data validation checks will be implemented and applied to the database on a regular basis. Queries are entered,

tracked, and resolved through the EDC system directly. The study database will be updated in accordance with the resolved queries. All changes to the study database will be documented in an audit trail.

2.2 Report Generation

The final statistical report will describe and justify any deviations from the original statistical analysis plan described herein. Analyses will be performed using SAS 9.4 software or most current version of R. All programs used to produce this report will be documented, tested, and archived and all tables, figures and listings will be validated before considered final.

2.3 Data Sets Analyzed

All analyses will be performed using a modified intent-to-treat (m-ITT) population, which is defined as all randomized subjects who took at least one dose of the study drug. Subjects who are discontinued from study drug temporarily or permanently are encouraged to complete all remaining study visits and will remain in the analysis population according to ITT. Subjects will be analyzed according to the treatment arm to which they were randomized. The safety population will be used to summarize all safety measures and is identical to the m-ITT population. The primary efficacy analysis will be repeated in the per-protocol population, which is defined as subjects having completed >70% of study drug doses based on subject diary and having incurred no major protocol violations. The per-protocol analyses will analyze subjects according to the treatment they received.

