13 PROTOCOL VIOLATIONS

A protocol violation occurs when the subject, investigator, or the Sponsor fails to adhere to significant protocol requirements affecting the inclusion, exclusion, subject safety and primary endpoint criteria. Protocol violations for this study include, but are not limited to, the following:

- Failure to meet inclusion/exclusion criteria
- Failure to obtain weight at either Visit 2 (or Combined Visit 1 and Visit 2) or Visit 4
- Use of prohibited concomitant medication that impacts the safety of the subject or is anticipated to significantly affect the primary endpoint
- Inappropriate administration of study drug that impacts the safety of the subject or inappropriate dispensing of study drug (e.g., a subject randomized to the placebo arm is given GSH)

Failure to comply with Good Clinical Practice (GCP) guidelines will also result in a protocol violation. The Sponsor will determine if a protocol violation should result in early permanent discontinuation of study treatment for a subject.

When a protocol violation occurs, it will be discussed with the investigator and a Protocol Violation Form detailing the violation will be generated. This form will be signed by a Sponsor representative and the Investigator. A copy of the form will be filed in the site's regulatory binder and in the Sponsor's files. The site will report the violation to their IRB in accordance with their IRB reporting requirements.

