15.5 Analysis of Safety Endpoints

All reported treatment emergent SAEs and AEs will be coded using MedDRA and grouped by body system. Treatment emergent AEs are defined as AEs presenting post study treatment initiation. SAEs and AEs will be tabulated by treatment group using standard coding terms sorted by body system. The incidence of AEs in each treatment arm will be tabulated by severity.

The number of SAEs and AEs will be summarized for each treatment group as follows: (i) The proportion of subjects with at least one (S)AE, (ii) The average number of (S)AEs per patient, and (iii) The rate of (S)AEs per patient week of follow-up. Histograms showing the frequency of the number of (S)AEs in each treatment group will be included. Rates of (S)AEs by System Organ Class (SOC) will be presented by treatment group. Poisson regression modeling will be used to derive rate ratios and 95% CIs comparing overall S(AE) rates by treatment group as well as within each SOC. The rate ratios will be compared using a two-sided 0.05 level test for Poisson count data.

Safety lab data at Visit 2 and Visit 4 and changes from baseline will be summarized by treatment group. In addition, the following clinical laboratory summaries will be presented by treatment group: (i) the incidence of clinically significant abnormalities at each study visit; and (ii) tables summarizing the frequencies of subjects below, within, and above the normal reference ranges at baseline and end of study; and (iii) tables displaying baseline to end of study shifts in each laboratory value (shifts between below, within or above normal range).

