2.4 Definitions

Baseline:

For participants with a combined Visit 1 and Visit 2, baseline refers to the combined visit (Day 0) when they were randomized. For participants with a separate Visit 1 and Visit 2, baseline refers to Visit 2 (Day 0) when they were randomized.

Study drug:

Study drug refers to the drug the participant was randomized to (either oral glutathione or placebo).

Treatment group:

Treatment group refers to participants randomized to either oral glutathione or placebo.

Follow-up time in weeks:

Follow up time in weeks will be calculated as the number of days from baseline to the final follow-up visit (approximately Week 24) or withdrawal date, divided by 7.

Follow-up time in months:

Follow up time in months will be calculated as the number of days from baseline to the final follow-up visit (approximately Week 24) or withdrawal date, divided by 30.4.

3. Overview of Planned Analyses

Unless otherwise noted, Poisson regression models with an offset for log of observation time will be used to derive rate ratios and corresponding 95% confidence intervals comparing treatment groups. Confidence intervals for differences in proportions between treatment groups will be calculated using the Newcombe-Wilson method without continuity correction and, where applicable, p-values for differences in proportions will be obtained from Fisher's exact tests.

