3.5 Adverse Events

Both the number of adverse events (AEs) and serious adverse events (SAEs) will be summarized by treatment group. The total number of (S)AEs, rate of (S)AEs per participant-month of follow-up, the average number of (S)AEs per participant, and the number of participants with at least one (S)AE will be provided. The number of (S)AEs per participant in each treatment group will be graphically represented as well as the proportion of participants in each treatment group experiencing at least one (S)AE by System Organ Class (SOC). Event counts and number of participants will be summarized for each SOC and (S)AE Preferred Term (PT) by treatment group, rates of (S)AEs by SOC will also be summarized. The number and percent of adverse events occurring will also be tabulated by severity.

The corresponding descriptive summaries and analyses are outlined in Appendix A, Section A.5 and a listing of serious adverse event narratives will be provided in Appendix B.

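### Safety tables follow the randomized arm, so if a placebo child were given GSH in error, that child's events on GSH would be counted under placebo

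*SAP*

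**What the plan says.** SAP 2.3 sets the rule in two consecutive sentences. The first covers who is counted where: "Subjects will be analyzed according to the treatment arm to which they were randomized". The second covers membership of the safety set: "The safety population will be used to summarize all safety measures and is identical to the m-ITT population". Protocol 15.1.1 says the same.

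SAP 2.4 then fixes the vocabulary: "Treatment group refers to participants randomized to either oral glutathione or placebo". It defines study drug in the same way, as the product assigned at randomization.

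The safety tables use that vocabulary. SAP 3.5: "Both the number of adverse events (AEs) and serious adverse events (SAEs) will be summarized by treatment group". Protocol 15.5: "SAEs and AEs will be tabulated by treatment group using standard coding terms sorted by body system". Protocol 15.5 also summarizes safety laboratory data by treatment group, and SAP 1.2 does so for the adverse event tables sent to the data monitoring committee.

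Treatment received appears in one place only: "The per-protocol analyses will analyze subjects according to the treatment they received" (SAP 2.3, also Protocol 15.1.1). In the SAP those analyses cover the primary efficacy endpoint; in the protocol they also cover key secondary analyses. Neither document extends them to safety.

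Protocol 13 lists inappropriate dispensing among the violations and gives the example "a subject randomized to the placebo arm is given GSH".

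**The concern.** A safety table is meant to show what happened to children exposed to each product. Under the stated rule, a placebo child who was dispensed GSH stays in the placebo column, together with any event that occurred on GSH. The contrast between arms is then pulled towards zero or, for a rare event, can point the wrong way. The trial is small and paediatric, so one child with one serious event can determine a row of the table.

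The plan names the error as an example violation and has an as-received rule, but attaches that rule to an efficacy sensitivity analysis and not to safety. The mechanism is credible: Protocol 8.3.3 describes identical bottles with a label that does not distinguish the products, and site pharmacists dispense at Visit 2 and again at Visit 3.

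**Working it through.** **1. Arm size.** Protocol 15.9 gives SD 0.4, effect 0.36, 90% power and a total of 54; Protocol 15.1 gives a two-sided 0.05 level. The standardized effect is 0.36/0.4 = 0.9. The normal approximation gives 26 per arm (52 in total). The t-test gives 26.94, so 27 per arm and 54 in total, with power 90.1%. The plan's 54 is reproduced. Allowing 10% attrition, 54/0.90 = 60, which at equal allocation (Protocol 8.1) is about 30 per arm. The sample size is not in question; it only supplies the 30 used below.

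**2. Which rule governs the safety tables.** The sentence equating the safety and m-ITT populations fixes membership only. The allocation of children to columns comes from the sentence before it and from the SAP 2.4 definitions. Together with the by-treatment-group tabulation in SAP 3.5 and Protocol 15.5, these leave no as-received reading for adverse events.

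**3. Expected effect.** Assume 30 per arm, m placebo-randomized children who take GSH throughout, and no errors in the other direction. Let pG and pP be the true risks on GSH and placebo.

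- Placebo column as randomized: [m·pG + (30 − m)·pP]/30
- Difference as randomized: (pG − pP)·(1 − m/30)

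The relative shrinkage is m/30, whatever the risks. With illustrative risks of 30% and 10% (assumed; the documents give none):

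| m | Shrinkage | Difference as randomized |
|---|---|---|
| 0 | 0% | 20.0 points |
| 1 | 3.3% | 19.3 points |
| 2 | 6.7% | 18.7 points |
| 3 | 10.0% | 18.0 points |

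**4. Worst case for one child.** The misdispensed child has an event that no other child has.

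- As randomized: 0/30 GSH versus 1/30 placebo, difference −3.3 points.
- As received: 1/31 GSH versus 0/29 placebo, difference +3.2 points.
- Shift: 1/30 + 1/31 = 0.0333 + 0.0323 = 0.066, or 6.6 points, with a change of sign.

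**5. The same child when the event is not unique** (assumed counts; the child is one of the placebo events).

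- 9/30 versus 4/30 becomes 10/31 versus 3/29: 16.7 to 21.9 points, a shift of 5.2.
- 24/30 versus 24/30 becomes 25/31 versus 23/29: 0 to 1.3 points, a shift of 1.3.

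So 6.6 points is the upper end. It applies to a rare event that the misdispensed child actually has.

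**The case against.** The best reply is that this depends on an error for which the documents give no rate. The entry in Protocol 13 is a single example in a generic list, and a reader might infer from it that the sponsor expects such errors. It shows only that the error was named as possible. That limit stands: without an error nothing changes.

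Second, much would be visible anyway. Protocol 13 requires a form for each violation, SAP 3.3 lists all violations, SAP 3.5 provides serious adverse event narratives, and Protocol 8.2 allows unblinding for serious unexpected suspected reactions. A reader might infer that harms on GSH would simply vanish; for a recognized error they would not. None of these steps, however, changes the tabulated proportions or the Poisson rate ratios. SAP 2.2 allows justified deviations in the final report, but a rule fixed in advance is preferable to one chosen after unblinding.

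Third, a reader might quote 6.6 points as the effect of any misdispensed child with an event. Steps 3 and 5 show that it is not.

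Fourth, the contrast with the per-protocol rule is weaker than it looks. That set excludes major violations, and major is not defined. A misdispensed child may be excluded, leaving the as-received rule there with little to act on.

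Fifth, counting any GSH dose as GSH is not free of error. If the wrong bottle came only at Visit 3 (Week 12), about 12 weeks of true placebo events and follow-up would move into the GSH column.

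**Conclusion.** The point holds as a conditional weakness in a stated rule. Safety is tabulated by assignment, and nothing in either document reassigns a child who took the other product. The expected effect is small, about 3.3% of the risk difference per misdispensed placebo child with an assumed 30 per arm. It reaches 6.6 points with a reversed sign only for an event seen in that child alone. It is zero if no dispensing error occurs. This is a low-severity point, worth settling because it is cheap.

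Two stronger readings are not supported. The protocol and SAP do not contradict each other here; they state the same safety rule. Nor do they clearly intend to drop a child who took only the wrong product. Read literally, SAP 2.4 makes study drug the randomized product, so such a child would have taken no dose of it and could fall outside the m-ITT and safety sets. That is a gap in drafting, which the revised wording below closes.

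**What to change.** In SAP 2.3, with SAP 2.4 and Protocol 15.1.1 aligned:

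- Define the safety population as all randomized subjects who took at least one dose of either product, and analyse it by treatment actually received.
- Pre-specify a rule for children who received both products. One option assigns events and follow-up time to the product being taken in each dispensing period (Visit 2 to 3, Visit 3 to 4). Another classifies any GSH exposure as GSH and flags events that precede the first GSH dose.
- Identify in the safety tables each child whose assigned and received treatments differ.
- Keep the m-ITT efficacy analyses by randomized arm.

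The cost is a few sentences and slightly more programming, mainly for the mixed-exposure rule. If an error occurs, safety and efficacy denominators may differ and will need a footnote. Sample size and the primary analysis are unchanged.
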